#### **15.5. Interim Analysis**

No interim analyses are planned for this study.

## **16. QUALITY CONTROL AND QUALITY ASSURANCE**

### **16.1. Protocol Amendments**

No changes from the final approved (signed) protocol will be initiated without the prior written approval or favorable opinion of a written amendment by the IRB/EC, except when necessary to eliminate immediate safety concerns to the study subjects or when the change involves only logistics or administration. The principal investigator and the sponsor will sign the protocol amendment.

### **16.2. Protocol Violations**

A **protocol violation** is defined as any divergence from the protocol-specific inclusion/exclusion criteria, subject is administered a prohibited medication, and/or GCP guidelines. Protocol violations will be identified and recorded, by study center personnel, on the CRF.

As a matter of policy, sponsor/CRO will not grant **exceptions** to protocol-specific entry criteria to allow patients to enter a study. If under extraordinary circumstances such action is considered ethically, medically, and scientifically justified for a particular patient, prior approval from sponsor/CRO and the responsible IRB/IEC, in accordance with the Sponsor/CROs Standard Operating Procedure (SOP), is required before the patient will be allowed to enter the study. If investigative center personnel learn that a patient who did not meet protocol eligibility criteria was entered in a study (a protocol violation), they must immediately inform sponsor/CRO. Such subjects will be discontinued from the study, except in a rare instance following review and written approval by sponsor/CRO and the responsible IRB/IEC, according to the applicable SOP.

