### **8.3. Removal of Subjects from Study Therapy**

A subject may be removed from the study therapy for a variety of reasons, including:

- Unacceptable adverse event
- Subject unwilling or refusal to continue with the protocol defined study visits and/or consent withdrawal for study participation
- Change in compliance with an inclusion/exclusion criteria
- Use of a prohibited medication (through Visit 13)
- General or specific changes in the subject's condition that render the subject unacceptable for further treatment in this study in the judgement of the investigator.

If a subject is to be withdrawn from the study, the Aclaris Therapeutics, Inc. CRA or designee must be informed within 24 hours of the decision to remove the subject from the study.

The study may be discontinued at the discretion of Aclaris Therapeutics, Inc. Some examples of reasons for discontinuation are the occurrence of the following:

- Increased frequency, severity or duration of known AEs
- Medical, regulatory or ethical reasons affecting the continued performance of the study
- Difficulties in the recruitment of subjects

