#### **8.4. Withdrawal Procedures**

If a subject withdraws from the study prior to Visit 13, the reason for and the date of withdrawal from the study must be recorded on the eCRF. If the reason for withdrawal is an adverse event or a clinically significant abnormal laboratory test result, monitoring of the subject will continue until the event has resolved or stabilized, until the patient is referred to the care of a local health care professional, or until a determination of a cause unrelated to the study drug or study procedure is made.

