#### **14.2.3. Withdrawal Due to an Adverse Event**

Any patient who experiences an adverse event may be withdrawn from study drug at any time at the discretion of the investigator. If a patient is withdrawn wholly or in part because of an adverse event, both the adverse events page and termination page of the CRF will be completed at that time. The patient will be monitored until the event has resolved or stabilized, until a determination of a cause unrelated to the study drug or study procedure is made, or until the patient is referred to the care of a local health care professional. The investigator must inform the medical monitor as soon as possible of all patients who are being considered for withdrawal due to adverse events. Additional reports must be provided when requested.

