### **15.2. Analysis of Populations**

The populations used for analyses will be defined as follows:

- Intent-to-Treat Population (ITT): The ITT population includes all randomized subjects.
- Per-Protocol Population (PP): The PP Population includes all subjects who received at least one application of study medication and have no major protocol violations.
- Safety Population: The Safety population includes all subjects who received at least one application of study medication.

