### **15.3. Statistical Analysis of Efficacy**

The ITT population will be used for primary and secondary efficacy analyses and summaries. The ITT population is defined as all subjects randomized to the study and analyzed as randomized. The Per-Protocol (PP) population will be used for sensitivity analyses for the primary efficacy analysis and all secondary efficacy analyses included in the hierarchical testing procedure. Details on all analyses discussed below will be provided in the study Statistical Analysis Plan (SAP).

The primary efficacy analysis will be a treatment comparison of A-101 45% compared to Vehicle at Visit 10 (Day 60). It will be based on the proportion of subjects who achieve complete clearance (PWA=0) of all identified common warts. A Cochran Mantel Haenszel (CMH) test stratified by the baseline number of treated warts will be used to perform the primary

efficacy comparison between treatment groups, with 2-tail alpha set at 0.05. The analysis will be based on the ITT population. Any identified common wart for a randomized subject that has missing data at the endpoint visit will be treated as not Clear for the purpose of the primary efficacy analysis.

The first sensitivity analysis for the primary endpoint will be an analysis based upon the PP population. This analysis will use the same CMH model described for the primary analysis. A second sensitivity analysis will be conducted for the primary endpoint using the same CMH model for the ITT population that includes the imputation of missing PWA data using a fully conditionally specified (FCS) regression-based Multiple Imputation (MI) procedure. To assess the impact of missing data imputation on the primary analysis results a tipping point analysis will be conducted. This analysis will shift the treatment coefficient in the regression model used in the MI procedure to impose a worse mean maximum PWA for the A-101 45% arm and a better mean maximum PWA for the vehicle arm. Details of this tipping point analysis will be specified in the SAP. In addition, a model similar to the primary analysis model but stratified instead by Study Center will be performed as a sensitivity analysis including a Breslow-Day test to evaluate heterogeneity across sites.

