##### **3.1.2 Subject Disposition and Discontinuation from Study**

The number of subjects screened, randomized and treated will be presented together with the study completion status and the reasons for discontinuation grouped by treatment and by major reason (lost to follow-up, adverse event, poor compliance etc.).

A listing will be provided of all patients discontinued from the study after enrolment, broken down by center and treatment group, giving a patient identifier, the specific reason for discontinuation, the treatment (drug and dose), and the duration of treatment before discontinuation. Whether or not the blind for the patient was broken at the time of discontinuation will be noted. Demographic and Baseline Characteristics  
Demographic and baseline characteristics will be presented in the data listings.

Descriptive summary statistics (n, mean, standard deviation, median, minimum, and maximum) and/or frequency distributions, as appropriate, will be generated by randomized treatment group and combined.

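### Conduct rules that end follow-up for randomized subjects create avoidable missing PWA outcomes, which the ITT analysis scores as not clear

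*Protocol*

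**What the plan says.** **Conduct**

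- Ineligible after entry (Protocol 16.2): "Such subjects will be discontinued from the study, except in a rare instance following review and written approval by sponsor/CRO" and the responsible IRB/IEC. Nothing is said about outcome visits for these subjects, and there is no separate rule on their study medication.
- Adverse event (Protocol 14.2.3): "Any patient who experiences an adverse event may be withdrawn from study drug at any time at the discretion of the investigator". If that happens, "both the adverse events page and termination page of the CRF will be completed at that time". Only monitoring of the event follows.
- Protocol 8.3 is headed as removal from study therapy, but its procedure begins "If a subject is to be withdrawn from the study". One of its listed reasons, use of a prohibited medication, runs through Visit 13, well after the last scheduled application on Day 53.
- Protocol 8.4 says that after withdrawal for an adverse event or abnormal laboratory result "monitoring of the subject will continue until the event has resolved or stabilized" (or until referral or an unrelated cause is established). It does not mention PWA.
- SAP 3.1.2 tabulates study discontinuation "by major reason (lost to follow-up, adverse event, poor compliance etc".

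**Analysis**

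- Protocol 15.2: "The ITT population includes all randomized subjects".
- Primary endpoint (Protocol 15.3): "Any identified common wart for a randomized subject that has missing data at the endpoint visit will be treated as not Clear". The same rule applies at Visit 13, and SAP 3.2.4 assigns 0% for percent of warts cleared.
- SAP Appendix B admits unscheduled and early-termination assessments by study day: Day 54-69 counts as Visit 10, Day 122 or later as Visit 13.
- SAP 3.2.2 plans multiple imputation and a tipping-point grid as sensitivity analyses. Time to clearance is censored at the last assessment (SAP 3.2.6).

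**The concern.** The analysis keeps subjects whom the conduct rules send away. For late-found ineligibility this is explicit: the sponsor's rule, not the subject's choice, ends follow-up, and a missing result then counts as treatment failure. For adverse events the wording leaves a site free to close the subject's record when medication stops, with no instruction to collect a PWA later.

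Some missing outcomes in the primary and first two secondary endpoints would therefore be avoidable. If leaving is balanced, the observed difference shrinks. If it is unbalanced, the comparison shifts against whichever arm loses more subjects. The sensitivity analyses would also have more to impute than they need to.

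**Working it through.** **1. Who is affected.** The last scheduled application is Day 53 and the Visit 10 window opens on Day 54. An exit assessment made on or before Day 53 therefore cannot count as Visit 10. A subject who leaves after Visit 10 keeps the primary result and lacks only Visit 13, unless assessed on Day 122 or later. The problem is confined to leavers with no PWA in the window.

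**2. Inputs.** From Protocol 15.1 and 15.3: 250 per arm, two-sided alpha 0.05, a difference of at least 11 points in the all-clear rate, power above 90%. Not given, so assumed: the all-clear rate in each arm and the fraction f leaving without a PWA in the window.

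**3. Formulas.** Observed rate = p × (1 − f). Power = Φ[(d − 1.96·SE0)/SE1], where SE0 = √(2·p̄(1 − p̄)/250) and SE1 = √{[pA(1 − pA) + pV(1 − pV)]/250}.

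**4. The plan's figure.** At 20% vs 9%: p̄ = 0.145, SE0 = 0.0315, SE1 = 0.0311, so (0.11 − 1.96 × 0.0315)/0.0311 = 1.55 and power is 94.0%. Across assumed vehicle rates, with active 11 points higher: 3% gives 99.4%, 5% gives 98.1%, 9% gives 94.0%, 12% gives 90.2% and 15% gives 86.4%. The stated >90% reproduces for vehicle rates up to 12%. The separate 97% simulation cannot be rerun because the WART-203 counts are not in the documents.

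**5. Leavers scored not clear.**

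| Assumed rates | Leaving, active / vehicle | Difference (points) | Power |
|---|---|---|---|
| 15% vs 4% | 0 / 0 | 11.0 | 98.9% |
| 15% vs 4% | 3% / 3% | 10.7 | 98.6% |
| 15% vs 4% | 10% / 10% | 9.9 | 97.9% |
| 20% vs 9% | 0 / 0 | 11.0 | 94.0% |
| 20% vs 9% | 3% / 3% | 10.7 | 93.2% |
| 20% vs 9% | 10% / 10% | 9.9 | 91.0% |
| 20% vs 9% | 10% / 5% | 9.45 | 87.8% |

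For the last row: 0.20 × 0.90 − 0.09 × 0.95 = 0.180 − 0.0855 = 0.0945.

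**6. Would observed outcomes restore the difference?** If leavers clear like the rest of their arm, yes: 11.0 points and 94.0% at 20% vs 9%. If active leavers clear only at the vehicle rate, no: with 10% leaving, 0.90 × 0.20 + 0.10 × 0.09 = 0.189, so the difference is 9.9 points and power 89.4%.

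**7. Direction under no treatment effect.** I simulated an unstratified CMH test with 200,000 runs per setting and true all-clear rates of 5% and 9% in both arms. With equal leaving, two-sided error stays at about 0.05. With 10% of active and 2% of vehicle leaving, the expected difference at 9% is 0.09 × (0.90 − 0.98) = −0.7 points, and false wins for A-101 fall to 0.013-0.015 against a nominal 0.025. With the pattern reversed they rise to 0.039-0.047.

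**The case against.** **Study exit after an adverse event.** A reader might infer that the protocol requires it. The text says withdrawal from study drug. Exit is suggested by the termination page and the event-only follow-up, but it is not written as a rule. Elsewhere the two ideas are kept apart: SAP 3.3.2 identifies events leading to treatment discontinuation by the action taken, and Protocol 10.5, 10.8 and 12.3 let a subject miss treatments without leaving. This objection stands. The adverse-event part is about unclear wording, and only Section 16.2 is explicit.

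**All leavers missing by rule.** This might also be inferred, but Appendix B contradicts it, and 16.2 has its approved exception.

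**Deliberate scoring, tested by sensitivity analyses.** Counting discontinuation as non-response is a recognised choice. The protocol, however, presents the scoring as handling of missing data, and an administrative removal for ineligibility says nothing about treatment failure. Multiple imputation and the 49-cell tipping-point grid test the assumption but supply model values. In the Appendix A code, a subject with no assessment from the Visit 8 window onward contributes only baseline PWA, wart count and arm.

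**Dropout is already allowed for.** Protocol 15.1 and SAP 3.5 say so, without a rate. The losses above therefore should not be read as a shortfall against the stated power.

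**Unequal withdrawal is not documented.** This is correct. Protocol 5.2 reports the Phase 2 treatment as well tolerated, with predominantly mild events. Eligibility is re-checked before randomization, so late-found ineligibility should be uncommon. The unequal scenarios show sensitivity and are not a forecast.

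**Conclusion.** The point holds as a low-cost improvement. Followed as written, Section 16.2 removes randomized subjects whose outcome could have been observed, and Sections 8.3, 8.4 and 14.2.3 leave it unclear whether subjects who stop medication are still assessed. A missing Visit 10 or Visit 13 result is then scored as not clear or 0%.

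The likely size is small. At 3-10% leaving equally, the loss is 0.3-1.1 points of difference, and power stays above 90% for both assumed pairs of rates. At an assumed vehicle rate of 12% power starts at only 90.2%, so there is little room there. At 20% vs 9%, leaving of 10% active and 5% vehicle gives about 88%. Bias could run either way. All of this rests on assumed leaving fractions and arm rates.

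Two stronger conclusions are tempting and unsupported. One is that the sample-size statement is wrong: the >90% figure reproduces for vehicle rates up to 12%, and dropout is said to be included. The other is that collecting outcomes would restore the lost power, which fails if active leavers clear at the vehicle rate. The gain is an ITT analysis that rests on observed outcomes.

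**What to change.** In Protocol 8.3, 8.4, 14.2.3 and 16.2:

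- State that stopping study medication is distinct from leaving the study, and record the two separately.
- Ask every randomized subject who has not withdrawn consent, including those found ineligible, to attend Visits 10 and 13 for PWA.
- Keep the not-clear and 0% rules for PWA that is truly missing, with multiple imputation and the tipping-point analysis unchanged.

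Whether medication is stopped in any of these situations is for the sponsor to reconcile across the four sections. Section 16.2 needs attention because it removes the subject from the study without a separate statement about medication.

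The cost is an amendment to wording, plus some extra follow-up and tracking of off-treatment subjects. Both visits are already in the schedule.

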### **16.3. Training**

For each investigational center, there will be an initiation visit prior to enrolling any study subjects.

It is strongly recommended that all investigators, other evaluators, study nurses, study coordinators or other applicable personnel attend this visit. During this visit, participants will be trained to the protocol, study specific procedures, and the CRFs. Those unable to attend the initiation visit must receive on-site training from an appropriately trained individual prior to participating in any of the procedures and evaluations in this study.

Clinical Research Associates (CRAs) and other applicable personnel will be trained prior to study initiation to familiarize CRAs with the disease, the Standard Operating Procedures (SOPs), the protocol and other study specific items. Team organization, communication and operational issues will also be discussed.

Aclaris Therapeutics, Inc. will provide an investigational center file to each center.

### **16.4. Monitoring**

The conduct of the study will be closely monitored by the Aclaris Therapeutics, Inc. study monitor /CRO to verify adherence to ICH Good Clinical Practice (GCP) guidelines, applicable SOPs, the protocol, other written instructions and regulatory guidelines.

The investigator will allow the Aclaris Therapeutics, Inc. representatives designee and/or and any regulatory agency to have direct access to all study records, CRFs, corresponding subject medical records, study medication dispensing records and study medication storage area, and any other documents considered source documentation. The investigator also agrees to assist the representative, if required.

## **16.5. Data Management**

Data will be collected using CRFs that are specifically designed for this study. The data collected on the CRFs will be captured in a clinical data management system (CDMS) that meets the technical requirements described in US 21 Code of Federal Regulations (CFR) Part 11. The CDMS will be fully validated to ensure that it meets the scientific, regulatory, and logistical requirements of the study before it is used to capture data from this study. Before using the CDMS, all users will receive training on the system and study specific training. After they are trained, users will be provided with individual system access rights.

The handling of data, including data quality assurance, will comply with regulatory guidelines, including ICH and GCP, and the sponsor/CRO SOPs and working instructions. Data management and control processes specific to this study will be described in a data management plan. At the end of the study, the database will be locked and the data will be released for reporting and statistical analysis.

## **16.6. Quality Assurance**

The study is conducted under the sponsorship of Aclaris Therapeutics, Inc. in compliance with the applicable regulatory requirements as well as applicable ICH guidelines, Helsinki Declaration, and in respect of the Aclaris Therapeutics, Inc. and/or sub-contractor SOPs for study conduct and monitoring.

Audits may be carried out by the Aclaris Therapeutics, Inc. or Aclaris Therapeutics, Inc.'s representatives and inspections may be performed by regulatory authorities or IRB/ECs before, during or after the study. The investigator will provide the auditing/inspecting group direct access to all study records (*e.g.*, CRFs, subject medical records, study medication dispensing records) and the investigational center study facilities. The investigator and study staff will be available and will assist the auditing/inspecting groups as appropriate.

## **16.7. Record Retention**

All pertinent data, samples, photographs, correspondence, original or amended protocol, reports and all other material relating to the study will be maintained securely in Aclaris Therapeutics, Inc./CRO/investigator archives for the legally required duration for archiving.

The investigator should maintain the essential study documents as specified in ICH GCP, and in compliance with all regulatory requirements. The investigator should ensure these documents are protected from accidental destruction or disposal.

If the Investigator needs to re-assign responsibility for maintaining these documents (*e.g.*, due to retirement) it must be transferred to a person willing to accept this responsibility. The

Aclaris Therapeutics, Inc.

Protocol Number: A-101-WART-302

Amendment 3: Version 5 14 February 2019

investigator must notify Aclaris Therapeutics, Inc., in writing, of the name and address of the new individual.

If the Investigator cannot guarantee this archiving requirement at the investigative site for any or all of the documents, special arrangements must be made between the Investigator and the Sponsor to store these in sealed containers in an off-site storage location so that they can be returned to the Investigator in case of a regulatory audit. Where source documents are required for the continued care of the patient, appropriate copies will be made for off-site storage.

No trial document should be destroyed without prior written agreement between the Sponsor and the Investigator. Should the Investigator wish to assign the trial records to another party or move them to another location, the Investigator must notify the Sponsor in writing of the new responsible person and/or the new location.

## **17. ETHICS AND GENERAL STUDY CONDUCT CONSIDERATIONS**

### **17.1. Institutional Review Board (IRB)/Ethics Committee (EC)**

This protocol and any accompanying material, including information that will be provided to prospective patients (such as advertisements, patient information sheets, or study descriptions used to induce study participation or obtain informed consent) must be submitted to the Central IRB for approval. Approval of each such submission must be obtained from the committee before it may be used in the study and must be documented in a written notification to the Investigator specifying the protocol number, protocol version, documents reviewed, and date on which the committee met and granted the approval. In particular, each informed consent document must bear clear evidence (written, stamp, date of approval, etc.) of IRB approval before it may be presented to prospective (or ongoing, as appropriate) study patients for signature.

Written evidence of the approval must be made available to the Sponsor. Any modifications made to the protocol and of correspondingly modified informed consent documents made after receipt of Central IRB approval must also be submitted to the committee for approval before implementation unless the modification is made on an emergency basis to protect the welfare of study patients. In the latter case, the Central IRB must be notified promptly and their written approval must be obtained as soon after the fact as possible.

Appropriate reports on the progress of the study will be made to the Central IRB and the Sponsor by the Investigator in accordance with applicable regulatory regulations and in conformity with policies established by both the Central IRB and the Sponsor. The shortest time interval between required reports required by either party or by regulations will prevail.

The Investigator at each investigative site, or his/her nominee, will be responsible for reporting any SAEs to the Central IRB as soon as possible, and in accordance with the guidelines of the Central IRB.

The Sponsor will be responsible for reporting all serious, life threatening or fatal adverse study drug events with a causal relationship to the study drug to appropriate regulatory agencies within their required timelines.

The Investigator is responsible for obtaining written, informed consent(s) from each prospective patient interested in participating in this study before performing any study-related procedures. Written informed consent must be obtained after adequate, thorough, and clear explanation of the aims, methods, objectives, and potential hazards of the study, as well as any use of the patient's genetic information from the study. The Investigator must use the most current Central IRB-approved consent form for documenting written informed consent. Each informed consent will be appropriately signed and dated by the patient and the person obtaining consent and each page not signed must be initialed and dated by the patient. The investigational site must retain the original signed consent and provide a copy to the patient.

